6.5 Study procedures

The FS-ICU questionnaire (Appendix 1) will be posted to family members, who consent to take part in the study, three weeks after the patient leaves the critical care unit. During the first month of recruitment only, family members of non-surviving patients will also be asked to complete the FS-ICU and QODD questionnaire (Appendix 2). One follow-up mailing will be conducted, four weeks after the original.

6.6 Assessments

6.6.1 Data collection

The following data will be collected from family members who consent to take part in the study to enable the FS-ICU questionnaire to be posted to them:

- title, initials and surname;
- postal address;
- their relationship to the patient.

In addition, brief demographic data (e.g. age group, ethnic group) will be collected to enable description of the study population.

The following data will be collected to enable the FS-ICU questionnaire to be sent to family member(s), who consent to take part in the study, three weeks after the patient is discharged from the critical care unit:

- date and time of patient admission to the critical care unit;
- date of patient discharge from the critical care unit or date of death in the critical care unit.

6.7 Data management

All data collected at participating units will be entered onto the FREE secure web-based data entry system and will be subject to validation checks built into the system. The PI will be responsible for timely and quality data. Collection and entry of data may be delegated to an appropriately trained member of the research team.

All electronic identifiable data will be encrypted and all study documents stored securely either at the participating unit (e.g. signed Consent Forms) or at the ICNARC Clinical Trials Unit (CTU) (e.g. completed FS-ICU questionnaires), as appropriate.

Family members will be asked to return completed questionnaires to the ICNARC CTU. Data from the questionnaires will be entered onto a secure database at ICNARC by trained members of staff. No identifiable information will be recorded on the FS-ICU or QODD questionnaires.

ICNARC is registered under the Data Protection Act 1998 and all ICNARC CTU staff undergo training in data protection and security and International Conference on Harmonisation (ICH) Good Clinical Practice (GCP).

6.8 Participant withdrawal

If a family member informs the PI or other staff members that they wish to withdraw from the study, then the PI or authorised staff member will be responsible for ensuring that all data are removed from the FREE secure web-based data entry system.

If a family member returns a questionnaire to the ICNARC CTU indicating that they no longer wish to take part in the study, then all identifiable information (i.e. name and address) will be removed from the FREE secure web-based data entry system and no further questionnaires will be sent.

7. Statistics

7.1 Sample size and recruitment rate calculation

The duration of recruitment will be one year, chosen to avoid bias from seasonal variation in case mix and workload. Data from the CMP database indicates that an average of 520 patients are admitted per unit, per year, and of these, 74% stay at least 24 hours, corresponding to 7,700 patients (approximately 19,250 family members). Assuming an average of 2.5 family members per patient and a 66% response rate,¹⁵ a total sample of approximately 12,700 responses, associated with 6,700 patients will be achieved. Using available FS-ICU data, published and unpublished, we anticipate mean baseline satisfaction domain scores of 80 with standard deviation 20. This sample size will give >90% power to detect ($p<0.01$) a binary patient factor present in 10% of the patient population associated with an increase or decrease in domain score of 4 points.

The sample size estimate was updated following completion of the first full quarter of recruitment, based on the CMP data submitted for that quarter from the actual participating sites and FREE Study data collected. Revised targets were calculated for each site based on successful recruitment of an average of 2 family members for 80% of patients staying at least 36 hours¹ in the critical care unit, allowing that on average 10% of patients may have no family members visit. Based on these revised targets, we anticipate recruitment of 14,200 family members (of 7,100 patients). Assuming a 60% response rate, a total sample of approximately 8,500 responses associated with 5,500 patients will be achieved. This sample size retains >90% power to detect ($p<0.01$) a binary patient factor present in 10% of the patient population associated with an increase or decrease in domain score of 4 points.

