Gaining patients' insights into adult critical care, however, poses an additional challenge. Each year, over 100,000 adults are admitted to adult, general critical care units in the NHS and approximately one third do not survive to leave hospital (yet the quality of the dying process is an important aspect of the humanity of critical care). In addition, predominantly because of the severity of their illness, but also due to the treatments used to support them, most patients are unable to participate in discussions regarding their care and, in those that survive, there is often little recollection of the experience in the critical care unit (<http://www.healthtalkonline.org> – patients' experiences of critical care). Family, therefore, play a vital role (<http://www.healthtalkonline.org> – family and close friends' experiences of critical care). Rather than restricting insights to a select subgroup of surviving patients who remember the critical care experience and relying on family to act as proxy respondents for those who do not, an alternative approach has been pursued: to seek the views of family directly, thus ensuring coverage for both surviving and non-surviving patients.

With greater recognition and acceptance of the contribution of patients, over the past two decades, there has been a large increase in the development of rigorous instruments (questionnaires) and a burgeoning research literature on their uses and benefits. Family satisfaction with critical care has been described as an abstract concept, by some; while others have gone on to describe it in some detail. The latter indicate that it reflects the extent to which perceived needs and expectations of the family members of critically ill patients are met by healthcare professionals and it may be influenced by many factors including families' expectations, information and communication, family-related factors (such as attitudes towards life and death, and social, cultural and religious background, etc.), hospital infrastructure and process of care.⁵ A number of tools have been developed but the most widely validated is the Family Satisfaction in the Intensive Care Unit questionnaire (FS-ICU),⁶ (Appendix 1) which assesses family satisfaction measuring two main conceptual domains: satisfaction with care and satisfaction with decision making.

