Variation in family satisfaction by: family member characteristics (e.g. relationship to the patient); patient/admission characteristics; unit/hospital characteristics; and other contextual factors will be explored using multilevel linear regression modelling. The outcomes for the regression models will be the two domain scores for satisfaction with care and satisfaction with decision-making. Models will be stratified by the survival status of the patient at discharge from the critical care unit. The levels of the model will be: level 1, family member; level 2, patient/critical care unit admission; level 3, unit/hospital. Family member characteristics entered into the models will include: age; sex; and relationship to the patient. Patient/admission characteristics will include: age; sex; severe chronic conditions in the past medical history; surgical status (elective surgery, emergency surgery, non-surgical); acute severity of illness (ICNARC Physiology Score¹⁹); and length of stay in the critical

care unit. Unit/hospital characteristics will include: teaching status; and number of beds in the critical care unit. Contextual factors will include: month of the year (seasonality). Non-linearity in the relationship between continuous predictors and satisfaction will be modelled using restricted cubic splines.

Variation in family satisfaction by country will be explored by comparing data collected for the FREE study with FS-ICU data from Canada (and available to [name]) in the context of a multilevel linear regression model with a similar structure to that above. Country comparisons will be adjusted for the age, sex and relationship to the patient of the family member and for patient characteristics consistently recorded in the different datasets.

As routinely surveying family members of all patients admitted to a critical care unit would neither be feasible nor cost-effective, understanding the association between patient factors and family satisfaction will enable an appropriately stratified sampling frame to be explored and developed.

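### The >90% power in 7.1 holds for the whole sample only; the survival-stratified models in 7.2 need their own figures, and the non-survivor model falls well short of 90%

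*Protocol*

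**What the plan says.** Section 7.1 of the protocol expects, after re-estimation, about 8,500 responses linked to 5,500 patients. On domain scores it says "we anticipate mean baseline satisfaction domain scores of 80 with standard deviation 20". It then makes a single power claim, for a 4-point change in either direction: "This sample size retains >90% power to detect ($p<0.01$) a binary patient factor present in 10% of the patient population". Both the sample and the 10% prevalence refer to all patients.

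Section 7.2 (Main analysis) sets out the multilevel linear models that relate each of the two domain scores to family member, patient, unit and contextual factors. Of these it says: "Models will be stratified by the survival status of the patient at discharge from the critical care unit". The levels are family member, patient and unit. No ICC is given, and neither stratum has a stated size or power.

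The only mortality figure is in section 2 (Background), which says of adults admitted to adult general critical care units that "approximately one third do not survive to leave hospital". This is hospital mortality; the proportion dying in the unit, which defines the strata, is not given.

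**The concern.** Section 7.1 gives the power of a comparison using every patient. The models that section 7.2 describes for patient factors are split by survival, which in its ordinary sense means one model for survivors and one for non-survivors. No patient-factor model using the whole sample is described, so the only power figure in the protocol does not belong to any of the planned patient-factor models.

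This matters most for families of patients who died. Section 2 gives coverage of non-surviving patients as a reason for surveying families at all, variation by patient characteristics is a stated objective in section 3, and section 7.2 builds the candidate sampling frames on the regression results. A reader who carries the >90% over to the non-survivor model would take a non-significant factor there as a well-powered negative finding, which it would not be.

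**Working it through.** **Inputs from the protocol.** Section 7.1: difference 4 points, SD 20, factor prevalence 10%, p<0.01, 5,500 patients, 8,500 responses (8,500/5,500 = 1.55 per patient). The test is taken as two-sided because the text counts an "increase or decrease in domain score of 4 points". Section 2: about one third die before leaving hospital.

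**Assumptions.**
- SD, prevalence and response rate are the same in both strata.
- There is no gain from covariate adjustment, and unit-level clustering is left out.
- The within-patient ICC is not given, so both limits are shown. With ICC = 1 the effective N is the number of patients; with ICC = 0 it is the number of responses.
- Deaths in the unit are a subset of deaths in hospital, so one third serves as a ceiling for the non-survivor share. It is approximate, because it covers all admissions and the study takes only stays over 24 hours.
- A 20% share is an illustration, not a figure from the protocol.

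**Formulas.**
- SE = 20 × √(1/(0.1N) + 1/(0.9N))
- Power = Φ(4/SE − 2.576)
- Difference detectable with 90% power = (2.576 + 1.282) × SE

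**The protocol's own figure.**
- N = 5,500: SE = 20 × √(1/550 + 1/4,950) = 0.90; power = Φ(4.45 − 2.576) = 97.0%.
- N = 8,500: SE = 20 × √(1/850 + 1/7,650) = 0.72; power = 99.8%.

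The stated >90% is therefore correct for a pooled analysis.

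**By stratum** (each cell: ICC 1 / ICC 0).

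| Analysis set | Effective N | SE | Power for 4 points | Detectable at 90% |
|---|---|---|---|---|
| Whole sample | 5,500 / 8,500 | 0.90 / 0.72 | 97.0% / 99.8% | 3.5 / 2.8 |
| Non-survivors, one third | 1,833 / 2,833 | 1.56 / 1.25 | 49.7% / 73.2% | 6.0 / 4.8 |
| Non-survivors, 20% (assumed) | 1,100 / 1,700 | 2.01 / 1.62 | 27.9% / 45.9% | 7.8 / 6.2 |
| Survivors, two thirds | 3,667 / 5,667 | 1.10 / 0.89 | 85.5% / 97.4% | 4.2 / 3.4 |
| Survivors, 80% (assumed) | 4,400 / 6,800 | 1.01 / 0.81 | 92.0% / 99.1% | 3.9 / 3.1 |

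**Share needed for 90% power.** The effective N required is about 4,140. That is 4,140/8,500 = 49% of responses (ICC 0) or 4,140/5,500 = 75% of patients (ICC 1), against a ceiling of about one third.

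**Sensitivity.**
- If the restriction to longer stays raised the non-survivor share to 45%, power would be 66% to 87%.
- If the test were one-sided, the one-third share would give 60% to 81%.
- If the factor were present in 20% of patients instead of 10%, the one-third share would give 80% to 95%. The shortfall is therefore specific to factors about as rare as the one in section 7.1.

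**The case against.** The best defence is that section 7.1 is right as it stands. It attaches the figure to the whole sample and the whole patient population, the figure reproduces, and it never promises 90% within each stratum. Stratifying also does not discard data: for an effect common to both strata, an inverse-variance combination of the two estimates would recover essentially the pooled precision. All of this is sound, and it is why a reader should not infer an arithmetic error. It does not remove the mismatch, because the protocol describes no pooled patient-factor model and no combination of strata, so a correct figure is left without a planned analysis to apply to.

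Separate models are also a defensible choice. Bereaved families have their own questionnaire items (Appendix 1, decision-making Q11 to Q13), and stratified against pooled modelling is a design preference. Nor is every regression split: the country model is only said to have a similar structure, and the adjusted funnel plots are not described as stratified.

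Some stronger inferences are tempting but not supported:
- That non-survivor power is as low as 20%. This needs a 15% unit mortality, which is nowhere in the protocol, together with ICC = 1.
- That the model would miss a true 4-point effect as often as it finds it. This is so at one third with ICC = 1 (49.7%), but not at 73.2%.
- That the non-survivor model cannot exclude a 4-point effect. At a one-third share the 95% half-width is 1.96 × 1.25 = 2.5 to 1.96 × 1.56 = 3.1 points, so an estimate near zero would exclude 4 points.
- That factors will be dropped from the sampling frames for lack of significance. The analysis is described as exploratory, no significance rule for selection is given, and survival status is already listed as a possible stratifier.

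**Conclusion.** The point holds as a mismatch of scope. The >90% in section 7.1 is a whole-sample figure (97.0% to 99.8%), while the patient-factor models in section 7.2 are stratified by survival. At the approximate one-third ceiling the non-survivor model has about 50% to 73% power for the stated effect; at any smaller share it has less. The survivor model lies between 85.5% and 97.4% at a two-thirds share, so it falls below 90% only towards the high-ICC end.

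The exact percentages rest on the unstated unit mortality and ICC, and on equal SD, prevalence and response rate across strata. The conclusion is sturdier than the percentages: even with fully independent responses, non-survivors would have to supply 49% of the sample to reach 90%. This should be fixed, but it invalidates neither the calculation nor the design.

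**What to change.** In section 7.1, state that the >90% power refers to an analysis of the whole sample. Add power, or the difference detectable with 90% power, for each survival stratum, using unit mortality from the CMP data and a stated within-patient ICC. The revised calculation already drew on CMP data from the participating sites, so the mortality input should be within reach. One further sentence should say that a non-significant factor in the non-survivor model is to be read from its confidence interval and not as a negative finding with >90% power.

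Optionally, add to section 7.2 a pooled model with survival status as a fixed effect and a common effect for each factor, without survival-by-factor interactions, and name it as the analysis to which >90% applies. The stratified models stay. The interactions need to be left out of that model: with them, a factor's main coefficient is its effect in the reference stratum, and the whole-sample power does not carry over to it.

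The cost is a few sentences and a short recalculation, with no extra participants or data. The figure shown for non-survivors will be less favourable than the one now in the text.

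### The stated >90% power holds for all relatives pooled, but the patient-factor models are split by survival; in the non-survivor models it is about 50–73% if one third of patients die

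*Protocol*

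**What the plan says.** Section 7.1 of the protocol updates the sample size after the first full quarter of recruitment. With 14,200 relatives recruited and a 60% response, "a total sample of approximately 8,500 responses associated with 5,500 patients will be achieved". The conclusion is that "This sample size retains >90% power to detect ($p<0.01$) a binary patient factor present in 10% of the patient population". The effect to be detected is 4 points in either direction, and the planning values are "mean baseline satisfaction domain scores of 80 with standard deviation 20". This is the only current power statement, and it refers to the whole expected sample.

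Section 7.2 (Main analysis) then describes the multilevel linear regressions of the two domain scores on family member, patient, unit and contextual factors, with levels for family member, patient and unit. On their structure it says: "Models will be stratified by the survival status of the patient at discharge from the critical care unit". No pooled patient-factor model is described, and no power or sample size is given for either survival group.

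Mortality at unit discharge, which defines the split, is not given. The only mortality figure is in section 2 (Background), for adult general critical care admissions: "approximately one third do not survive to leave hospital".

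**The concern.** The power statement and the planned models do not refer to the same set of observations. Section 7.1 counts every response; each model in section 7.2 uses only one survival group. The smaller group, the relatives of patients who died in the unit, gets a fraction of the sample, and the reader is not told what the study can detect there.

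This matters for two reasons. Section 2 gives coverage of non-surviving patients as a reason for surveying families at all. And section 7.2 builds the candidate sampling frames on the results of these regressions. A reader who applies >90% to the non-survivor models would treat a non-significant patient factor there as better evidence of no association than it is.

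**Working it through.** **Inputs from the protocol.** Section 7.1: 8,500 responses, 5,500 patients, SD 20, difference 4 points, significance level 0.01, factor prevalence 10%. The test is taken as two-sided because the effect may be an increase or a decrease. Section 2: one third of patients die before leaving hospital.

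**Assumptions.**
- Correlation between relatives of the same patient is not given. The two extremes are used: correlation 0, where each response counts as one observation, and correlation 1, where each patient counts as one.
- The non-survivor share is not given. One third is used as a proxy, and 15–25% as a sensitivity range that is not in the document.
- The 10% prevalence, the SD and the response pattern are taken as equal in both groups. Clustering by unit is left out.

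**Formulas**, with n the effective number of observations in the model:
- SE = 20 × √(1/(0.1n) + 1/(0.9n)) = 20/√(0.09n)
- power = Φ(4/SE − 2.576)
- difference detectable with 90% power = (2.576 + 1.282) × SE

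**Step 1: the plan's own figure.**
- n = 8,500: SE = 0.723, 4/SE = 5.532, power = Φ(2.956) = 99.8%.
- n = 5,500: SE = 0.899, 4/SE = 4.450, power = Φ(1.874) = 97.0%.

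The stated >90% is right for the pooled sample.

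**Step 2: observations needed in one model for 90% power.**
n = (20 × (2.576 + 1.282)/4)² / 0.09 ≈ 4,133. This is 4,133/8,500 = 49% of all responses at correlation 0, or 4,133/5,500 = 75% of all patients at correlation 1.

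**Step 3: the two groups at a one-third non-survivor share.**

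| Model | Correlation | n | SE | Power | Detectable with 90% power |
|---|---|---|---|---|---|
| Non-survivors | 0 | 2,833 | 1.253 | 73.2% | 4.8 points |
| Non-survivors | 1 | 1,833 | 1.557 | 49.7% | 6.0 points |
| Survivors | 0 | 5,667 | 0.886 | 97.4% | 3.4 points |
| Survivors | 1 | 3,667 | 1.101 | 85.5% | 4.2 points |

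**Step 4: sensitivity to the share (assumed values), non-survivor models.**

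| Share | n (correlation 1 to 0) | Power |
|---|---|---|
| 15% | 825 to 1,275 | 20% to 33% |
| 20% | 1,100 to 1,700 | 28% to 46% |
| 25% | 1,375 to 2,125 | 36% to 58% |

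**Step 5: sensitivity to equal prevalence.** Suppose the factor is present in 20% of non-survivors, so that 0.16 replaces 0.09 in the SE. At a one-third share, non-survivor power becomes 80% (n = 1,833) to 95% (n = 2,833). At a 20% share it is at most 76.5% (n = 1,700). If overall prevalence stays at 10%, prevalence in survivors at the one-third share must be (10% − 20%/3)/(2/3) = 5%. With 0.0475 in the SE, survivor power is then 53% (n = 3,667) to 76% (n = 5,667). The shortfall moves to the other model; it does not disappear.

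**The case against.** The strongest reply is that nothing is miscalculated. Section 7.1 speaks of the sample size as a whole and never promises >90% within each survival group, and the affected models are exploratory. The first part stands: this is a statement whose scope does not match the planned models, not an arithmetic error. But since no pooled patient-factor model is described, the figure has no planned analysis to attach to, so a label is needed.

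Several stronger readings are tempting and are not supported.

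- **Power as low as 20%.** This needs a 15% non-survivor share, which the protocol does not give. Nor is one third a proven ceiling: it is hospital rather than unit mortality, and it describes all admissions, whereas the cohort is limited to stays over 24 hours.
- **A true 4-point effect would be missed more often than found.** At one third, power runs from an even chance to 73%. The statement holds at assumed shares of 20% or less, and no passage makes those the more likely ones.
- **Every planned analysis is affected.** The country comparison is said only to have a similar structure, the adjusted unit funnel plots are not said to be split by survival, and the psychometric work is not stratified.
- **Null results will remove factors from the sampling strata.** The protocol contains no such rule. Section 7.2 gives age, sex, survival status and length of stay as example strata, includes unstratified frames, and judges frames by their correlation with full-population unit scores. The risk lies in how a reader interprets a null result.

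**Conclusion.** The point holds as a mismatch of scope with a real numerical consequence. The >90% is true for pooled relatives (97.0–99.8%) and not for the non-survivor models at any share below about 49% of responses; with correlated relatives the required share is higher still. On the only mortality figure in the document, non-survivor power is about 50–73% and survivor power about 85–97%, so even the survivor models are not certain to exceed 90%. At assumed shares of 15–25%, non-survivor power would be about 20–58%.

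These figures rest on hospital mortality as a proxy for the unit share, on within-patient correlation between 0 and 1, and on equal prevalence and SD in the two groups. The direction does not depend on the 15–25% range. Severity is moderate: the stated power needs correcting, but no estimate, analysis or recruitment target changes.

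**What to change.** In section 7.1:

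1. Say that >90% refers to all relatives pooled.
2. State, separately for the survivor and non-survivor models, either the power for 4 points or the difference detectable with 90% power. Use the non-survivor share observed in the first-quarter data and a stated within-patient correlation. The revision already drew on those data, and section 6.6.1 records death in the unit, so the share can be obtained. Do not write in figures that presume a share; those for 20%, for example, would be wrong at 15% or at one third.
3. Say whether prevalence and SD are assumed equal in the two groups.

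In section 7.2, add one sentence saying that non-significance in the non-survivor models is to be read against that detectable difference.

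The cost is a few lines of text and a less favourable stated power for relatives of patients who died. Recruitment is unchanged.
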